#### 8.2.4 Electrocardiograms

A single 12-lead resting ECG will be recorded after the patient has been in supine position for at least 5 minutes to calculate the heart rate and measure PR, QRS, QT, and QTc intervals. The results will be recorded in the eCRF. A trained clinical site physician will perform the clinical assessment of each 12-lead ECG. Additional 12-lead ECGs will be performed if judged to be clinically appropriate or if the ongoing review of the data suggests a more detailed assessment of ECGs is required.

NEVARINI	Corporate Medical Department		nent	
	Р	Protocol Templat State	e	
Identification Number	Version Number	State	Effective date	
FORM-000050125	2.0, CURRENT	Effective	08 Jan, 2021	

*Study Code:* MEIN/21/AmNe-Hyp/001

### 8.2.5 Urine Pregnancy tests

Urine pregnancy tests (when appropriate) will be performed at Visit 1, 2, 3, and 4, by determination of the urine  $\beta$  human chorionic gonadotropine, using locally available commercial dipsticks. Unscheduled re-tests can be performed as required according to the Investigator's judgment.

### 9 SAFETY DATA MANAGEMENT

### 9.1 Adverse Event

An AE is defined as any untoward medical occurrence in a patient or clinical trial patient administered a medicinal product and which does not necessarily have a causal relationship with this treatment.

An AE can therefore be any unfavorable and unintended sign (including an abnormal laboratory finding), symptom, or disease temporally associated with the use of a medicinal product, whether or not considered related to the medicinal product.

### 9.2 Drug Relationship

The causal relationship between an AE and study treatments will be judged according to the following categories:

**Certain**: The AE occurs in a plausible time relation to the administration of the drug and cannot be explained by a concurrent disease or other drugs or chemicals. The response to withdrawal of the drug (dechallenge) should be clinically plausible. The event must be definitive pharmacologically or phenomenologically, using a satisfactory rechallenge procedure if necessary.

**Probable**: The AE occurs in a reasonable time relation to the administration of the drug, it is unlikely to be attributed to a concurrent disease or other drugs or chemicals and it follows a clinically reasonable response on withdrawal (dechallenge). Rechallenge information (AE reappearance after drug reintroduction) is not required to fulfill this definition.

MENARINI	Corporate Medical Department		nent	
	P	Protocol Template		
Identification Number	Version Number	State	Effective date	
FORM-000050125	2.0, CURRENT	Effective	08 Jan, 2021	

*Study Code:* MEIN/21/AmNe-Hyp/001

**Possible**: The AE occurs with a reasonable time relation to the administration of the drug, but it could also be explained by a concurrent disease or other drugs or chemicals. Information on drug withdrawal (dechallenge) may be lacking or unclear.

**Unassessable**: The relationship cannot be judged, because of the information is insufficient or contradictory and cannot be supplemented or verified.

**Unlikely**: A causal relationship cannot be definitively ruled out, but: other drugs, chemicals, or underlying disease provide plausible explanations and/or the temporal relation to the administration of the drug makes a causal relation improbable.

Not Related: Any of the following are present:

- Existence of a clear alternative explanation, and/or
- Unreasonable temporal relationship between Drug and Event, and/or
- Non-plausibility.

## 9.3 Adverse Drug Reaction

An adverse drug reaction (ADR) is any untoward and unintended response to an investigational medicinal product (IMP) related to any dose administered.

The definition implies a reasonable possibility of a causal relationship between the event and the IMP. This means that there are facts (evidence) or arguments to suggest a causal relationship.

An ADR is considered any AE for which the relationship is considered as:

- Certain
- Probable
- Possible
- Unassessable

An AE is not considered as ADR when the relationship is judged as:

• Unlikely

MENARINI	Corporate Medical Department		ent
	]	Protocol Template	
Identification Number	Version Number	State	Effective date
FORM-000050125	2.0, CURRENT	Effective	08 Jan, 2021

Study Code: MEIN/21/AmNe-Hyp/001

• Not related

#### 9.4 Seriousness

An AE/ADR is considered serious when:

- Results in death
- Is life-threatening

Note: Life-threatening is considered any AE in which the patient was at risk of death at the time of the event; it does not refer to an event which hypothetically might have caused death if it were more severe.

- Requires inpatient hospitalization or prolongation of existing hospitalization.
- Results in persistent or significant disability/incapacity.
- Is a congenital anomaly/birth defect.
- Is another medically important condition that may jeopardize the patient or may require intervention to prevent one of the outcomes listed above. Any suspected transmission of an infectious agent via a medicinal product is considered serious and should be assessed under the category of medically important events in the absence of other seriousness criteria.

An AE/ADR is considered non-serious when it does not fulfill the conditions for the definition of SAE/ADR.

### 9.5 Adverse Event/Adverse Drug Reaction Intensity

The intensity level of a serious or a non-serious AE or ADR is attributed according to the following definitions:

Mild: does not interfere with routine activities; in case of laboratory tests, when there is a mild abnormality.

**Moderate**: interferes with the routine activities; in case of laboratory tests, when there is a moderate abnormality.

МЕМАНИИ	Corporate Medical Department		nt
	F	Protocol Template	
Identification Number	Version Number	State	Effective date
FORM-000050125	2.0, CURRENT	Effective	08 Jan, 2021

### *Study Code:* MEIN/21/AmNe-Hyp/001

Severe: makes it impossible to perform routine activities; in case of laboratory tests, when there is a significant abnormality.

## 9.6 Adverse Event/Adverse Drug Reaction Expectedness

An AE/ADR is considered unexpected when the nature, severity, or outcome of the AE/ADR is not consistent with the information provided in the Reference Safety Document (SmPC).

## 9.7 Serious Unexpected Adverse Drug Reaction (SUSAR)

Any SAE judged by the Investigator or the Sponsor as drug-related (see Section 9.3) and considered as unexpected qualifies as a SUSAR.

Serious Unexpected Adverse Drug Reactions are subject to expedited reporting, as specified in Section 9.10, as having a "Reasonable Possibility" of relationship with the IMP.

## 9.8 Individual Case Safety Report (ICSR)

Format and content provided to describe one or several AEs or a disease experience that occur to an individual patient at a particular point of time.

## 9.9 Collection, Recording and Reporting of AEs

At each visit the Investigator will collect and assess any subjective or objective AE occurred to each patient after his/her signature of the informed consent.

Any laboratory test abnormality (newly occurring after the study treatment administration or worsening of previously known abnormalities) that the Investigator considers as clinically relevant: ie. values significantly above or under normal range or which require an intervention or diagnostic tests or may result in the study treatment discontinuation will be reported as an AE.

Any AE(s) communicated by the patient or by the patient's relatives or delegates through phone calls, letters or e-mails will also be collected and assessed.

The Investigator shall record on the respective eCRF AE recording pages/AE form any recognized AE identifying an ICSR, both serious and non-serious, whether or not thought to

MENARINI	Corporate Medical Department		ient	
	Р	Protocol Templato	;	
Identification Number	Version Number	State	Effective date	
FORM-000050125	2.0, CURRENT	Effective	08 Jan, 2021	

*Study Code:* MEIN/21/AmNe-Hyp/001

be drug-related, observed in or reported by the patient (or relatives/delegates), specifying the judgment on the causal relationship with the study treatment.

Any available information and diagnostic measure (laboratory and instrumental tests, procedures, etc.) shall be recorded in and/or attached to the concerned eCRF pages/sections.

The Investigator is also expected to record any AE which is ongoing at the last treatment dose and a follow-up phone call will be made after 2 weeks from the last study visit. The Investigator is expected to follow-up until the outcome of the AE has been determined.

The Investigator must report all the collected information on any ICSR including seriousness (whether or not thought to be related to the investigational drug), providing the concerned eCRF AE pages by alert e-mail, after the first knowledge of the occurrence of the case, to:

CRO Pharmacovigilance Officer: Will be reported through CRO's Pharmacovigilance group (AmNe\[contact]) for which its details will be provided via study guidelines.

The eCRF pages concerning IMP, medical history, concomitant medication, and laboratory tests should also be sent to the Sponsor by e-mail.

## 9.10 Management of Serious AEs (SAEs) including laboratory abnormalities

### 9.10.1 Reporting Duties of the Investigator

If the Investigator becomes aware of a SAE with a suspected causal relationship to the investigational medicinal product that occurs after the end of the clinical trial in a patient treated by him or her, the Investigator shall, without undue delay, report the SAE to the Sponsor.

The Investigator must report all the collected information on any serious ICSR (whether or not thought to be related to the investigational drug), as specified above, no later than 24 hours after the first knowledge of the occurrence of the case.

Any further information and supporting documentation that become available (copies of laboratory reports, tests, procedures, autopsy evidence of the cause of death, etc.) shall be

MENARINI	Corporate Medical Department		ent
		Protocol Template	
Identification Number	Version Number	State	Effective date
FORM-000050125	2.0, CURRENT	Effective	08 Jan, 2021

*Study Code:* MEIN/21/AmNe-Hyp/001

provided no later than 24 hours after the knowledge, by the Investigator to the CRO by alert e-mail, to be forwarded to the Sponsor.

The Investigator must also comply with the local applicable obligation(s) on the reporting of ADRs to the local concerned Regulatory Authority/EC.

## 9.10.2 Reporting Duties of the Sponsor

The Sponsor shall ensure that all relevant information about any SUSAR, is expeditiously reported to the competent authorities and ECs as required, with these deadlines after the first knowledge, intended as the day when the CRO receives the notification of the SUSAR:

- Fatal and life-threatening unexpected cases, no later than 7 days.
- Other unexpected serious cases, no later than 15 days.

The Sponsor shall ensure that all relevant information and supporting documentation that subsequently becomes available, is also expeditiously reported as follow-up information according to the above-mentioned deadlines.

Furthermore, the following safety issues will be subjected to expedited management for the identification of possible necessary actions:

- SAEs associated with the trial procedures.
- Potential clinically significant findings emerging from non-clinical studies.
- An anticipated end or suspension for safety reasons of another trial with the same study treatment.

When appropriate and applicable the Sponsor will arrange the adequate information to be communicated to the Investigators.

For trials in high morbidity and/or mortality disease, where efficacy endpoint could also be serious unexpected ADR or when a fatal or other serious outcome is the primary efficacy endpoint, agreement with competent authority will be reached to treat SAE as disease-related and not subjected to expedited reporting.

MENARINI	Corporate Medical Department		nt
		Protocol Template	
Identification Number	Version Number	State	Effective date
FORM-000050125	2.0, CURRENT	Effective	08 Jan, 2021

*Study Code:* MEIN/21/AmNe-Hyp/001

### 9.11 Management of Non-serious AEs including laboratory abnormalities

### 9.11.1 Reporting Duties of the Investigator

The Investigator must report all the collected information on any non-serious AE ICSR (whether or not thought to be related to the investigational drug), as specified above, no later than 5 calendar days after the first knowledge of the occurrence of the case.

Any further information and supporting documentation that become available (copies of laboratory reports, tests, procedures, etc.) shall be provided no later than 24 hours after the Investigator first becomes aware, to the CRO by e-mail or fax, to be forwarded to the Sponsor.

### 9.12 Management of any laboratory abnormality

Any laboratory test abnormality which occurs after IMP administration and is considered by the Investigator as an AE, is to be managed as above detailed (refer to Section 9.9). However, all "out of range" values should be collected and reviewed periodically (modality to be established) by the CRO and the Sponsor.

### 9.13 Management of pregnancy exposure cases

The Investigator is expected to record in the provided form any case of pregnancy exposure occurring in a female patient or in a male patient's partner the treatment and follow-up periods, sending it within 5 days after being made aware of the pregnancy, to the CRO by e-mail or fax, to be forwarded to the Sponsor.

The Investigator is requested to follow each case of pregnancy exposure until the outcome.

If the pregnancy results in an abnormal outcome, this will be recorded in the eCRF as a SAE and managed as above described.

Eligibility of a woman of childbearing potential (WOCBP) will be considered as described in Section 6.2.1. A woman is considered fertile following menarche and until becoming postmenopausal unless permanently sterile as described below.

MENARINI	Corporate Medical Department		ent
	Р	rotocol Template	
Identification Number	Version Number	State	Effective date
FORM-000050125	2.0, CURRENT	Effective	08 Jan, 2021

*Study Code:* MEIN/21/AmNe-Hyp/001

Women in the following categories are not considered WOCBP if:

- Premenarchal
- Premenopausal female with one of the following:
  - Documented hysterectomy.
  - Documented bilateral salpingectomy.
  - Documented bilateral oophorectomy.

Note: Documentation can come from the study site personnel's review of the patient's medical records, medical examination, or medical history interview.

• Postmenopausal female: A postmenopausal state is defined as no menses for 12 months without an alternative medical cause. A high follicle stimulating hormone (FSH) level to 30 mIU/mL or higher may be used to confirm a postmenopausal state in women not using hormonal contraception or hormonal replacement therapy (HRT). However, in the absence of 12 months of amenorrhea, a single FSH measurement is insufficient. Females on HRT and whose menopausal status is in doubt will be required to use one of the non-estrogen hormonal highly effective contraception methods if they wish to continue their HRT during the study. Otherwise, they must discontinue HRT to allow confirmation of postmenopausal status before study enrolment.

### **10 WITHDRAWAL CRITERIA**

### Withdrawal of monotherapies or the study treatment

Withdrawal from the monotherapies or study treatment refers to any patient who does not receive the complete course, ie. when no further planned dose is administered from the date of withdrawal. A patient withdrawn from the monotherapies or study treatment may continue further study procedures (safety) planned in the Study Protocol, as deemed appropriate by the Investigator once the safety of the patient is recovered/reassured.

A patient's study treatment or monotherapies may be discontinued for any of the reasons below. In addition to the scheduled visits, patient who have been withdrawn from study treatment or monotherapies may also undergo additional medical follow-up at the discretion of the Investigator.

MENARINI	Corporate Medical Department Protocol Template		ent
Identification Number	Version Number	State	Effective date
FORM-000050125	2.0, CURRENT	Effective	08 Jan, 2021

#### *Study Code:* MEIN/21/AmNe-Hyp/001

- Any AE, which required treatment termination according to the Investigator's judgment.
- Clinically significant intercurrent illness or laboratory results which could compromise the safety of the patient or the scientific value of the study.
- Investigator deems it to be in the best interest of the patient to discontinue.
- Requirement to use prohibited medication that could compromise the safety of the patient or the scientific value of the study.

### Withdrawal of patient from the study

The patient may withdraw from the study at any time without explanation, without losing the right to future medical care. The participation of the patient may, at any moment, be terminated by the Investigator, if considered appropriate.

A patient can be withdrawn during the study for any of the following reasons:

- Any AE, which required treatment and study termination for the patient according to the Investigator's judgment.
- Abnormal renal function or liver enzyme parameters as described in Section 8.2.3.
- Patient becomes pregnant during the study.
- Request of the patient (without giving any reason).
- Investigator deems it to be in the best interest of the patient to discontinue.
- Failure to adequately comply with the dosing, evaluations, or other requirements of the study.
- If the patient meets an exclusion criterion (newly developed or not previously recognized) that precludes further study participation.
- Use of any prohibited medication that in the opinion of the Investigator or Sponsor necessitates the patient being withdrawn.

The reason for the withdrawal of study treatment, or withdrawal from the study must be well documented in the source documents and in the eCRF page and should capture the date and the specific underlying reason for discontinuation of study treatment or patient discontinuation/withdrawal.

MENARINI	Corporate Medical Department		
	Р	Protocol Template	
Identification Number	Version Number	State	Effective date
FORM-000050125	2.0, CURRENT	Effective	08 Jan, 2021

*Study Code:* MEIN/21/AmNe-Hyp/001

Patients who discontinue from the study early will be asked, anyway, to complete all the assessments of Visit 4. Patients may discontinue the study treatment, but remain in the study for follow-up, especially for safety study endpoints (if applicable).

If a patient has been discontinued/withdrawn due to an AE, the Investigator must immediately notify the relevant pharmacovigilance contact (see Section 9.9) and should be followed-up until the AE is resolved or the Investigator deems further observations or examinations as no longer medically indicated.

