## 7.6 Not permitted medications

The following drugs modifying BP, even if used for other indications, are considered Prohibited medications and the patients will not be permitted to use these medications from screening until the end of treatment:

Blood pressure modifying drugs including

- Alpha receptor blockers and agonists.
- Beta receptor blockers and agonists.
- Calcium antagonists.
- Angiotensin converting enzyme inhibitors.
- Diuretics.
- Centrally acting antihypertensive (eg. clonidine, methyldopa, guanfacine).
- Reserpine.
- Moxonidine.
- Chronic nitrate treatment (eg. isosorbide dinitrate or isosorbide mononitrate).
- Phosphodiesterase inhibitor and angiotensin II receptor blockers.

Moreover, special attention should be paid to contraindicated/not-recommended drugs as per Nebivolol and Amlodipine SmPCs, in particular the CYP3A4 inductors and inhibitors.

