### 12.5.2 Primary (efficacy) analysis

The primary efficacy analysis will be conducted on the mITT population. The results will be interpreted for the same population.

The primary endpoint is the change in mean sitting DBP between Visit 2 (Week 0) and Visit 4 (Week 8).

MENARINI	Corporate Medical Department		
	Р	rotocol Template	
Identification Number	Version Number	State	Effective date
FORM-000050125	2.0, CURRENT	Effective	08 Jan, 2021

*Study Code:* MEIN/21/AmNe-Hyp/001

The statistical hypothesis will be defined as below:

H0: There is no change in the sitting DBP prior or post combination therapy.

H1: There is a difference in the sitting DBP prior or post combination therapy.

The above hypothesis will be tested as following:

- Change from baseline in sitting DBP from prior and post combination therapy will be tested using paired t-test. The p-value obtained from the paired t-test will be presented.
- Assumption of Normality will be investigated using Wilk-Shapiro test. If the data is found to be non-Normal, the paired t-test will be replaced by Wilcoxon signed rank test.
- The primary endpoint will be summarized descriptively using n, mean, median, SD, Q1, Q3, minimum, and maximum.

Additionally, a repeated measure general linear model (GLM) will be performed on the primary efficacy endpoint (change in mean sitting DBP) to test the covariate effects and the effects of interactions between the covariates. Age, gender, body mass index, and baseline DBP will be included in the GLM model as covariates. The GLM model will be explained in detail in the Statistical Analysis Plan (SAP), approved before database lock.

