5.2. Modified Intent-to-Treat (mITT) Population

The Modified Intent-to-Treat (mITT) population will contain all patients who are in the Enrolled population, receive at least one dose of combination therapy, and have at least baseline and Week 8 assessments with primary efficacy data.

Document: \\eedc-vnasc01\Biosdata\Menarini\NebAml\ZZA67778\Biostatistics\Documentation\SAP\SAP_Menarini_MEIN21AmNe-Hyp001_Final_V1.0

Author: [name]

Version Number:

Final V1.0

Version Date:

11Nov2022

Template No.: CS_TP_BS016 Revision 7

Reference: CS_WI_BS005

Effective Date: 01Nov2021

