16.1.2. Intercurrent Event Handling and Data Imputation for Primary Efficacy Variable

Not Applicable.

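### The SAP has no rule for Visit 4 blood pressures taken after another BP-lowering drug was added or the combination was stopped, and the per-protocol analysis only partly covers the gap

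*Protocol*

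**What the plan says.** **Other BP drugs.** Protocol 7.6 lists BP-modifying drugs and says "the patients will not be permitted to use these medications from screening until the end of treatment". Protocol 7.7 has no rescue medicine. Protocol Section 10 deals with use in two places. Among the reasons why treatment may be discontinued is "Requirement to use prohibited medication that could compromise the safety of the patient or the scientific value of the study". Among the reasons why a patient can leave the study is "Use of any prohibited medication that in the opinion of the Investigator or Sponsor necessitates the patient being withdrawn". Both leave the decision to judgement.

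**Stopping treatment.** Section 10 lets a patient come off study treatment and remain in follow-up, mainly for safety. It also states: "Patients who discontinue from the study early will be asked, anyway, to complete all the assessments of Visit 4".

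**Who is analysed.** SAP 5.2 puts into mITT the enrolled patients who "receive at least one dose of combination therapy, and have at least baseline and Week 8 assessments with primary efficacy data". SAP 16.1.3 adds that DBP must be available at Weeks 4 and 8. Neither section requires the patient to be on treatment, or free of other BP drugs, at Visit 4. Protocol 12.5.2 ties the conclusion to this set: "The primary efficacy analysis will be conducted on the mITT population. The results will be interpreted for the same population".

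**Intercurrent events.** SAP 16.1.2, headed "Intercurrent Event Handling and Data Imputation for Primary Efficacy Variable", is answered as not applicable. SAP 7.3 uses observed data only.

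**Sensitivity analysis.** SAP 16.1.5 repeats the primary analysis in the PP set. SAP 5.4 removes major deviations that could affect the primary analysis. SAP 9.2 has deviations reviewed one at a time before database lock. No criterion mentions prohibited BP drugs.

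**The concern.** All patients follow one sequence, monotherapy and then combination, with no randomisation (Protocol 12.1). The whole change from Visit 2 to Visit 4 is read as the effect of the combination. There is no second arm in which added drugs would also occur and partly cancel. If a patient on the combination also takes, say, a diuretic before Visit 4, the fall it causes enters the primary estimate. If the reading falls below 130/80 mmHg, the patient also counts as a goal success.

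The SAP does expect such events elsewhere. SAP 15.1 has a compliance rule for patients who permanently stop study medication, and SAP 18.1.2 tabulates events leading to discontinuation. Marking intercurrent events as not applicable is therefore inconsistent with the plan's own content. SAP Section 2 has estimands in its title but states none, so the reader cannot tell whether the target is the effect while on the combination or the result under whatever the patient ended up taking.

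**Working it through.** Falls in DBP are written as positive numbers.

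**1. The plan's own figure.** Protocol 12.2 assumes a mean fall of 4 mmHg, a null value of 2, SD 10, 5% significance and 90% power, giving 216.
- Difference tested: 4 − 2 = 2 mmHg.
- One-sided 5%, normal approximation: (10 × (1.645 + 1.282) / 2)² ≈ 214.2, so 215. The noncentral t gives 216, with power 90.1%. The figure reproduces.
- Two-sided 5% would need 265, with power 83.3% at 216.

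The yardsticks are thus an assumed effect of 4 mmHg and a sizing difference of 2 mmHg.

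**2. Patients who stay on the combination and add a drug.** Let f be the share affected and e the extra DBP fall. The documents give neither, so both are assumptions. Bias in the mean fall = f × e.

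| f (patients of 216) | e = 5 mmHg | e = 10 mmHg |
|---|---|---|
| 3% (about 6) | 0.15 | 0.30 |
| 5% (about 11) | 0.25 | 0.50 |
| 10% (about 22) | 0.50 | 1.00 |

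As a share of the 2 mmHg sizing difference: 0.15/2 = 7.5% up to 1.0/2 = 50%.

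Effect on the false-positive rate at n = 216, holding SD at 10:

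| Bias | One-sided 5% test against 2 (as sized) | Two-sided 5% test against 0 (as coded in SAP Appendix 1) |
|---|---|---|
| 0.5 mmHg | 18.1% | 11.3% |
| 1.0 mmHg | 42.9% | 31.0% |

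**3. Patients who stop and take nothing else.** If a share f shows zero change, the mean is 4 × (1 − f).
- f = 5%: 3.8 mmHg, one-sided power against 2 falls to 84%.
- f = 10%: 3.6 mmHg, 76%.
- f = 15%: 3.4 mmHg, 66%.

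Zero is itself an assumption. Baseline is measured on monotherapy (SAP 6.2), so a patient who stops both drugs may end above baseline.

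**4. Patients who stop and take a substitute.** The change is the substitute's effect minus the lost monotherapy effect. It may be large, small or negative. The formula f × e does not apply.

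**5. What each analysis would show.** Illustration with a true fall of 4, f = 5% staying on the combination, and e = 8:
- mITT as observed: 4 + 0.05 × 8 = 4.4.
- PP, if all affected patients are excluded: 4.0.
- PP, if none are excluded: 4.4.
- Affected patients set to change = 0: 0.95 × 4 = 3.8.

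**6. Early leavers.** Protocol Section 10 asks for their Visit 4 assessments. SAP 6.3 uses nominal visits in by-visit summaries and names early-discontinuation data for listings. SAP Appendix 1 has a separate early-termination label. No text says whether these readings count as Week 8.

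**The case against.** The strongest reply is that such cases should be few. The drugs are prohibited, needing one is a listed reason to stop treatment, and uncontrolled BP at Visit 3 already leads to uptitration within the protocol. Deviations are reviewed before lock, concomitant drugs are tabulated (SAP 13), and the PP analysis stands as a check. This has weight: the 3–10% is unsupported by the documents, and the 1.0 mmHg figure is its extreme corner. But rarity is not a rule. Neither set of withdrawal reasons makes withdrawal automatic, and the conclusion rests on mITT.

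Three stronger readings are tempting but not supported.
- **That mITT and PP both err in the favourable direction, so PP cannot reveal the problem.** Step 5 shows that deleting patients with an extra fall can move PP below mITT, so the contrast is informative. PP could also lose patients who responded poorly to the combination alone. The defect that can be shown is the missing exclusion criterion.
- **That stopping the combination inflates the result.** Without a substitute it pulls towards no change or beyond.
- **That a patient who stops the combination and substitutes another drug adds that drug's full effect.** The observed change also carries the loss of the earlier monotherapy.

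**Conclusion.** The gap is real. The plan retains Visit 4 readings taken after an added BP-lowering drug or after stopping the combination, and has no stated strategy for either. The path is clear for patients who stay in the study to the nominal Visit 4 and have a Week 4 reading; for early leavers the documents are ambiguous.

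For patients who remain on the combination and add a drug, the bias favours the combination: 0.15–1.0 mmHg under the assumed 3–10% and 5–10 mmHg. The Visit 4 goal rate could be overstated by at most the same 3–10 percentage points, and only if every such patient reaches goal and none would have done so otherwise. Stopping without a substitute works against the combination. The net direction and size cannot be derived from the documents, and the PP analysis is a partial check. This should be corrected before database lock, but it does not show that the primary result will be favourable by a known amount.

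**What to change.** Replace the entry in SAP 16.1.2 with two defined events:
- (a) use of a BP-lowering drug from the Protocol 7.6 list, other than study treatment, that is ongoing at Visit 4 or recent enough to affect that reading. Fix the time limit before database lock. The definition should say BP-lowering because the 7.6 list also includes agonists, and without a time limit one early dose would count.
- (b) permanent stop of the combination before Visit 4.

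Then:
- In SAP 16.2.2.3 and 16.3.2, count patients with either event as not at goal at Visit 4.
- Keep the as-observed mITT test as the primary analysis. Add one pre-specified sensitivity analysis for DBP and SBP with change = 0 for patients with either event. Call it a conservative convention, not an estimate of their true change, and state it as an exception to SAP 7.3.
- Name event (a) as a PP exclusion in SAP 5.4.
- State whether Visit 4 assessments done at early termination count as Week 8.
- Report the number of patients with each event.

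Do not make the primary conclusion depend on both analyses agreeing. That would change the primary decision rule, which Protocol 12.5.2 places on mITT, and Protocol 12.7 requires a substantial amendment for changes to the primary analyses.

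The cost is SAP wording and one extra table. The inputs are already collected: concomitant medication (SAP 13), last study medication date (SAP 14), and the date and reason for discontinuation (Protocol Section 10). The sensitivity estimate and the goal rate may come out slightly less favourable.
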